5.2.3 Follow-up Visits

After enrollment in the study, we will measure medication adherence in both arms at 3 month intervals for 12 months. MLVI, the standard deviation of recorded drug levels, will be calculated for each subject. Medication adherence will be ascertained through electronic health record (EHR) review of immunosuppression levels (i.e. tacrolimus, sirolimus, cyclosporine, prednisone, mycophenolate). Organ transplant recipients get labs post-transplant drawn frequently. Included in these lab draws are immunosuppression levels. A significant change in trough levels (i.e. undetectable or supra therapeutic) signal an issue of adherence to the prescribed regimen (i.e. missing doses, taking extra doses, etc.). We will track lab values using EHR, and record these in the secure REDCap database.

Participants in both arms will complete the immunosuppressant therapy instrument (ITAS), a validated tool to measure medication adherence at baseline for those subjects who have been on immunosuppressant therapy for at least 3 months at time of enrollment, at 12 weeks post enrollment for all subjects, and at 12 months post enrollment. Scores on the ITAS scale range from 0 (very poor adherence) to 12 (perfect adherence), and scores will be compared between the control and intervention arms (25). Participants will complete age appropriate QOLs at matching intervals to the ITAS. Follow-up questionnaires will be completed by phone with a designated study team member. Indicate treatment and followup visit assessments for each visit. List all measurements and procedures in bulleted format.

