4. SELECTION AND ENROLLMENT OF PARTICIPANTS

4.1 Inclusion Criteria

Participants must meet all of the following inclusion criteria to participate in this study:

- ≥ 13 years old
- Own a smartphone and are willing to receive information through it
- Received a liver or kidney transplant at a participating study site during or prior to the study period.

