4.3 Study Enrollment Procedures

Participants will be approached by the following methods:

For subjects ages 13-21 years old: either while they are an inpatient post-transplant or at any follow-up outpatient clinic visit by a study member to participate in this study.

For subjects >21 years old: either while they are an inpatient post-transplant or at their first post-op outpatient clinic visit by a study team member to participate in this study.

For all subjects:

When feasible to conduct in-person consenting, written consent will be obtained explaining the purpose of the study, their part in it, and that they can withdraw from the study at any time. As much time as necessary will be allowed for obtaining consent. Assent will be obtained from participants age 13-17 years, along with parental consent.

Additionally, we will make provisions for phone consent and enrollment if needed due to potential COVID-19 restrictions so that enrollment may proceed according to plan. If unable to conduct in-person consenting and enrollment process, patients will be contacted by phone and the study team will conduct the appropriate oral consent/assent procedures and conduct the procedures listed below remotely.

We will use block randomization to assign participants to the intervention or the control group using random block sizes ranging from 2 to 8. Block randomization will improve the probability of balanced groups over the course of the study as well as during shorter time horizons. A research data analyst, blind to the group allocations, will generate a list of sequential group assignments using this method. The list will be used to create sequentially numbered, sealed envelopes that will be used to allocate consenting participants to the control or intervention arms of our study. Each patient will have a 50% chance to be in the intervention arm of the study.

Participant enrollment will continue until we have reached 25 participants in each arm by age (13-21 years and 22 years and older) for a total of 100 participants and we will follow study participants for 12 months. No study visits are required of research participants after enrollment, but they will complete surveys and an interview over the phone.

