9. STATISTICAL CONSIDERATIONS

Primary outcome variables:

12-week immunosuppression medication adherence:

We will measure medication adherence in both arms at 12 weeks. The Medication Level Variability Index (MLVI) will be used to analyze immunosuppression lab

values to determine adherence with a relative risk noted for standard deviation >2 .

Secondary outcome variables:

- Hospitalization days
- Biopsy-proven rejection
- Clinician-assigned rejection

We will recruit 100 liver and kidney transplant recipients (50/arm), and compare recipients who received the mHealth intervention to controls that did not receive it. The Medication Level Variability Index (MLVI) will be used to analyze immunosuppression lab values to determine adherence with a relative risk noted for standard deviation >2 . Descriptive statistics will be performed to compare frequencies of secondary outcomes (e.g., hospitalization, rejection, etc). Patient reported outcomes will be scored as appropriate and differences compared between treatment arms. Additionally, we will perform subgroup analyses for younger transplant recipients (age at transplant <40), older transplant recipients, men, and women.

In addition to understanding the efficacy of this technology in a transplant patient population, we will also evaluate the feasibility of implementing such a system into clinical workflow. We will examine time spent by reviewers each week using mDOT, most ideal time post-transplant to consent and educate participants on using the application, and streamlining the workflow involved in the application. In order to ensure acceptability among the patients who will be using the app, we will survey all participants in the intervention arm at the end of the study period on their overall satisfaction in using the app. This survey will be administered with the ITAS scale over the phone. In addition, we will also examine consent rate and use of the mDOT app by participants over time to understand acceptability of using the application.

Feasibility will also be measured through phone interviews with all study participants at 12 months. We will contact all patients who consented to be in the study to participate in the phone interviews. The interviews will be semi-structured, with a set of pre-written questions as the guide. All interviews will be audio recorded. Transcription of the interviews will be conducted by Production Transcripts, Inc.

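### In participants over 21 the 12-week MLVI falls in the early post-transplant months and cannot separate ordered dose changes from missed doses, so the app effect may be diluted and the plan could not detect it

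*Combined protocol and SAP*

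**What the plan says.** **Measure.** Section 5.2.3 states that "MLVI, the standard deviation of recorded drug levels, will be calculated for each subject". It adds that marked changes in trough level "signal an issue of adherence to the prescribed regimen (i.e. missing doses, taking extra doses, etc".

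**Primary outcome.** Section 9 sets the time point: "We will measure medication adherence in both arms at 12 weeks". It uses MLVI on the laboratory "values to determine adherence with a relative risk noted for standard deviation >2".

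**Timing of entry.** Section 4.3 differs by age. Those over 21 are approached "either while they are an inpatient post-transplant or at their first post-op outpatient clinic visit by a study team member". Those aged 13-21 are approached "either while they are an inpatient post-transplant or at any follow-up outpatient clinic visit by a study member". The quota is 25 per arm in each of two age groups (13-21, and 22 and over), so half of the planned 100 participants enter under the narrower rule.

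**What is not there.** No section says that ordered dose changes will be recorded, that the SD will be taken within periods of constant dose, or that the comparison will allow for time since transplant. Section 5.2.3 does restrict the baseline ITAS to participants at least 3 months on immunosuppression, but it sets no similar condition for MLVI.

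**The concern.** MLVI measures spread around a single mean per participant. If the prescriber changes the dose within the window and the mean level moves, the two dose periods are pooled into one larger SD. A participant who took every dose can then be counted as non-adherent.

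The participants most exposed are those over 21. On the plain reading, their whole primary window follows directly on the transplant.

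The stated objective is adherence. If the primary measure partly records prescribing in half of the sample, a null or weak result could not be interpreted: it might mean that the app does not work, or that the measure was swamped by ordered changes. Without dose-change dates, the data would not show which.

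**Working it through.** **The plan's own figure.** 25 × 2 arms × 2 age groups = 100, as stated. The plan gives no power, event rate or effect size, so nothing further can be reproduced.

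**Inputs from the documents.** The SD > 2 threshold and relative risk at 12 weeks (section 9), the plain SD (section 5.2.3), 50 per arm (section 9), and background non-adherence of 15-40% in adults and 50-70% in adolescents (section 2).

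**Assumed, because the documents are silent.** The number of levels per participant, the within-dose SD, the size of the level shift, the share of adherent participants falsely flagged (q), and the true effect.

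**Step 1: can an adherent patient cross the threshold?** Take levels 6, 6, 6 before an ordered change and 10, 10, 10 after it. The mean is 8 and each deviation is 2 in size, so SD = √(6 × 4 / 5) = √4.8 = 2.19. This uses the usual n − 1 divisor, which the plan does not specify. With divisor n the value is exactly 2.00, right at the cut.

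**Step 2: how often?** Simulation of a fully adherent patient with normal levels, 8 draws and one change after the fourth draw, giving the chance that the plain SD exceeds 2:

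| Shift in mean level | within-dose SD 1.0 | SD 1.2 | SD 1.5 |
|---|---|---|---|
| 0 | about 0% | 0.7% | 9% |
| 2 | about 4-5% | 13% | 31% |
| 3 | 34% | 46% | 60% |
| 4 | 82% | 83% | 86% |

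The answer depends heavily on the shift, and a change that leaves the mean level where it was adds nothing.

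**Step 3: effect on the relative risk.** Suppose every truly non-adherent participant is flagged, and a share q of adherent ones is flagged in both arms. Then the observed rate is p + (1 − p)q. With assumed true rates of 30% and 15% (relative risk 0.50):

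- Affected group: RR = (0.15 + 0.85q) / (0.30 + 0.70q).
- Whole trial, with only the 22-and-over half affected: RR = (0.30 + 0.85q) / (0.60 + 0.70q).

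| q | RR in affected half | RR overall |
|---|---|---|
| 0 | 0.50 | 0.50 |
| 0.1 | 0.235/0.370 = 0.64 | 0.385/0.670 = 0.57 |
| 0.3 | 0.405/0.510 = 0.79 | 0.555/0.810 = 0.69 |
| 0.5 | 0.575/0.650 = 0.88 | 0.725/0.950 = 0.76 |

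**Step 4: the same with rates from section 2.** Use mid-range control rates of 27.5% (older group) and 60% (ages 13-21), an assumed true RR of 0.50, two-sided alpha 0.05, and false flags in the older half only. The overall RR is 0.50, 0.55, 0.64 and 0.70 for q = 0, 0.1, 0.3 and 0.5. Power at 50 per arm is 65%, 60%, 51% and 45%.

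**Step 5: would a within-dose SD solve it?** Pool squared deviations from the mean of each dose period. For an adherent patient with two periods of four draws, the chance of exceeding 2 no longer depends on the shift. It is about 1% at within-dose SD 1.2 and about 10% at 1.5.

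Now take a non-adherent patient whose level falls by 4 units mid-window and stays down (SD 1.2, 8 draws). The plain SD flags about 83%. If the prescriber changes the dose one draw after the fall, the pooled SD flags about 35%. If the change coincides with the fall, it flags about 1%. The pooled SD removes false flags but can also remove true ones.

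**The case against.** The strongest reply is that the plan uses an index it describes as validated (section 1.1), that randomisation balances dose changes between arms, and that the size of the problem rests wholly on assumptions. A dose change made to hold a level on target need not shift the mean at all, and the 6-to-10 example is constructed.

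Much of this stands. The arms are expected to be equally affected, so the error is conservative. The documents give nothing from which to fix q. But balance does not prevent dilution, and the documents do not say that validation covered the first months after transplant. The plan would also leave q unknown after the trial, since dose changes are not to be recorded.

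Section 4.1 admits anyone who "Received a liver or kidney transplant at a participating study site during or prior to the study period", and an inpatient stay after transplant could include a later readmission. Eligibility is not the approach rule, however, and readmission is not the natural reading of section 4.3. Still, the statement about the early window rests on that reading.

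A reader might also infer that age and time since transplant are fully confounded. The documents do not support that: those aged 13-21 may also be enrolled as inpatients, and the planned subgroup cut is age 40 at transplant. The most that can be said is that anyone aged 40 or over at transplant entered under the narrower rule, while the younger subgroup is mixed. Comparisons between arms within a subgroup remain randomised.

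**Conclusion.** The point holds as a risk of dilution that the plan neither measures nor examines. As written, the plan can score adherent participants over 21 as non-adherent. Under the assumed 30% versus 15%, with q from 0.1 to 0.5, a true relative risk of 0.50 would appear as 0.57 to 0.76 overall. The figures of 0.64 to 0.88 apply only to the affected half and should not be read as trial-level.

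Two stronger readings go too far. One is that the trial is biased towards a false benefit: nothing in the documents suggests that ordered changes would differ by arm. The other is that the plain SD should be replaced as the primary measure. Dose changes occur after randomisation and may respond to missed doses, so conditioning on them can hide true non-adherence, as step 5 shows. Nor do the documents establish a cut of 2 for the pooled statistic.

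**What to change.** In section 9:

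1. Keep the planned all-levels MLVI with SD > 2 as the primary outcome.
2. Include time since transplant at enrolment as a factor in the primary comparison, split at under 3 months versus 3 months or more on therapy (the cut already used for the baseline ITAS). A stratified relative risk, such as Mantel-Haenszel, would do.
3. Have the extractors, blinded to arm as section 5.2.2 provides, record ordered dose-change dates from the same EHR.
4. Pre-specify the pooled within-dose-period SD as a sensitivity analysis, to be read alongside the primary and not in place of it.

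**Cost.** Some added extraction and a few lines of text, with no change to care or visits. The factor improves comparability and precision but does not itself remove the dilution. In the pooled SD each dose period costs one degree of freedom, periods with a single level contribute nothing, and the SD > 2 cut is borrowed. Because it can mask non-adherence that prompted a dose change, a difference between the two analyses shows that prescribing matters to the result but does not show which analysis is correct.

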6. RISKS AND BENEFITS

6.1 Risks

The only risk to participants in using this mHealth application is the loss of confidentiality, which will be kept to a minimum. This application will comply with HIPAA regulations on how to handle PHI, including but not limited to secure encryption of data, access controls, and industry-standard best practices. All information gathered will be de-identified and only linked through a study-specific identification number.

All study data except identifying information will be entered into a central access database (REDCap). These data will be accessible by only authorized study personnel

from the secure study database. User level authentication will be required to gain access to the REDCap account. A separate access database will be created which has patient identifiable information along with a unique identifier. All specific assessments will have labels (individual study ID number) affixed to them and the results will remain strictly confidential. Risks to confidentiality will be minimized by separating identifiers from the results of the questionnaires.

6.2 Benefits

Participants may or may not benefit directly from participation in this study. Participation in the study could help providers, transplant centers, and liver transplant recipients in the future from the information gathered in this study.

6.3 Renumeration

Subject will receive \$100 after completion of participation.

6.4 Costs

There is no cost to patients for participating in this study.

7. SAFETY ASSESSMENTS

This is a minimal risk study. However, there is a slight risk of loss of confidentiality. To minimize this risk, hard copies of all study materials, including consent forms, will be stored in locked cabinets that are only accessible to the study team. Electronic copies of all study materials will be kept on a secure, password-protected server that is only accessible to the study team. All study data except participants' identifying information will be entered into a central access database. These data will be accessible by only authorized study personnel from the secure study database. User level authentication will be required to gain access to the central database. A separate access database will be created which has patient identifiable information along with a unique identifier. All specific assessments will have labels (individual study ID number) affixed to them and the results will remain strictly confidential. Risks to participants' confidentiality will be minimized by separating identifiers from the results of the survey responses.

8. INTERVENTION DISCONTINUATION

Participants may withdraw from the study at any time without penalty. This would not preclude participants from obtaining regular medical care or follow-up care related to their transplant. If participants choose to withdraw, the study team will use the data collected prior to withdrawal and mark the remaining data as censored.

Upon study completion or if study participation ends prematurely, those who were randomized to mDOT app will return to their usual standard of care. Those who were randomized to standard of care will continue in that manner.

9. STATISTICAL CONSIDERATIONS

Primary outcome variables:

12-week immunosuppression medication adherence:

We will measure medication adherence in both arms at 12 weeks. The Medication Level Variability Index (MLVI) will be used to analyze immunosuppression lab

values to determine adherence with a relative risk noted for standard deviation >2 .

Secondary outcome variables:

- Hospitalization days
- Biopsy-proven rejection
- Clinician-assigned rejection

We will recruit 100 liver and kidney transplant recipients (50/arm), and compare recipients who received the mHealth intervention to controls that did not receive it. The Medication Level Variability Index (MLVI) will be used to analyze immunosuppression lab values to determine adherence with a relative risk noted for standard deviation >2 . Descriptive statistics will be performed to compare frequencies of secondary outcomes (e.g., hospitalization, rejection, etc). Patient reported outcomes will be scored as appropriate and differences compared between treatment arms. Additionally, we will perform subgroup analyses for younger transplant recipients (age at transplant <40), older transplant recipients, men, and women.

In addition to understanding the efficacy of this technology in a transplant patient population, we will also evaluate the feasibility of implementing such a system into clinical workflow. We will examine time spent by reviewers each week using mDOT, most ideal time post-transplant to consent and educate participants on using the application, and streamlining the workflow involved in the application. In order to ensure acceptability among the patients who will be using the app, we will survey all participants in the intervention arm at the end of the study period on their overall satisfaction in using the app. This survey will be administered with the ITAS scale over the phone. In addition, we will also examine consent rate and use of the mDOT app by participants over time to understand acceptability of using the application.

Feasibility will also be measured through phone interviews with all study participants at 12 months. We will contact all patients who consented to be in the study to participate in the phone interviews. The interviews will be semi-structured, with a set of pre-written questions as the guide. All interviews will be audio recorded. Transcription of the interviews will be conducted by Production Transcripts, Inc.

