Participants will be enrolled in the study for 12 months. All subjects will complete study assessments and have immunosuppressant levels and clinical outcomes followed for 12 months. Subjects randomized to the intervention group will use the app for the first 3 months following enrollment. Subjects randomized to the control group will not use the app and will follow routine standard of care.

No study visits are required of research participants after enrollment, but they will complete surveys and an interview over the phone.

Procedure	Baseline	3 months	6 months	9 months	12 months
Baseline clinical/demographic/lab info/baseline survey	X				
Immunosuppression levels and laboratory values collected from medical record	X	X	X	X	X
Interval health information collected		X	X	X	X
Patient-reported outcomes*	X	X			X
Phone Interview					X

*these include ITAS, PedsQL <18 years at enrollment or SF-36 if >18 years at enrollment, Reikert self-efficacy scale, PSSUQ (treatment arm only and only at 3 months)

Sample Size and Population:

Participant enrollment will continue until we have reached 25 participants in each arm by age (13-21 years and 22 years and older) for a total of 100 participants. We will follow all study participants for 12 months.

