1. STUDY OBJECTIVES

1.1 Primary Objective

To compare medication adherence of solid organ transplant recipients, specifically liver and kidney transplants, using the mobile DOT (mDOT) application (i.e., intervention) to those who did not use the mDOT application (i.e., control). We will compare medication adherence between intervention and control arms using the Medication Level Variability Index (MLVI), a validated measure of adherence derived from the standard deviation of measured drug levels (22-23).

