2. BACKGROUND AND RATIONALE

In adolescent and adult solid organ transplant recipients, poor adherence to immunosuppressant medications carries the risk of graft rejection, short- and long-term post-transplant complications, and increased healthcare costs (1-8). In transplant recipients, adherence to immunosuppressive drugs, as well as general medical indications is imperative to overall outcomes (9). The rate of non-adherence to immunosuppressive medications in transplant patients varies vastly, with reports ranging from 15-40% in adults and much higher at 50-70% among adolescents (9-14). Additionally, medication adherence is a key concern in the transition from adolescent to adult-centered transplant care, and transition planning should be prioritized in these transplant patients (15-18). Because of lacking objective and accurate non-adherence measurements, both to immunosuppressive drugs and medical indications, the true implications and prevalence of non-adherence is not yet well understood (19-21). Therefore, we believe that mobile health (mHealth) technology has the potential to allow clinicians and researchers to more comprehensively address and understand non-adherence in adolescent and adult transplant recipients.

emocha Mobile Health Inc. has developed an application that enables users to track dose-by-dose medication adherence through asynchronous, video directly observed therapy (DOT). This helps patients take their medication as prescribed and gives providers the assurance that their patients are supported and successful in treatment. DOT is the practice of watching a patient take every dose of medicine in-person, and has typically only been done in extreme cases because it can be both costly and burdensome: DOT is the standard of care for Tuberculosis treatment and has proven high-adherence rates. Through mHealth technology, DOT can be used more broadly and without added burden; emocha's technology allows this through enabling patients to use their mobile application

to view their regimen, record themselves taking every dose of their medication, report side effects or symptoms, visualize their treatment progress, and access educational content. This information is encrypted and transmitted to a HIPAA-secure web portal for providers to review. The aim of this study is to conduct a randomized control trial to compare medication adherence between patients who use the mHealth system against controls who do not.

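### The primary adherence index is an unscaled SD with one unitless cut, and no index drug, unit or multi-drug rule is stated, so it partly measures drug and level scale

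*Combined protocol and SAP*

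**What the plan says.** - **Objective (Section 1.1).** "We will compare medication adherence between intervention and control arms using the Medication Level Variability Index (MLVI"), which is described as "a validated measure of adherence derived from the standard deviation of measured drug levels (22-23"). The citation is the only further detail. It brings no drug, unit or scaling into the text.
- **Definition (Section 5.2.3).** "MLVI, the standard deviation of recorded drug levels, will be calculated for each subject". The next sentence reads "Medication adherence will be ascertained through electronic health record (EHR) review of immunosuppression levels (i.e. tacrolimus, sirolimus, cyclosporine, prednisone, mycophenolate"). The same paragraph adds that "A significant change in trough levels (i.e. undetectable or supra therapeutic) signal an issue of adherence to the prescribed regimen".
- **Primary outcome (Section 9).** At 12 weeks the MLVI "will be used to analyze immunosuppression lab values to determine adherence with a relative risk noted for standard deviation >2". This covers liver and kidney recipients together, 50 per arm.
- **Eligibility (Sections 4.1 and 4.2).** No criterion restricts the immunosuppressive regimen.

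**The concern.** An SD carries the unit and size of the values it is taken from. A single cut of 2, or an uncut comparison of raw SDs, puts patients on a common scale only if they share a drug, a unit and a similar level. The plan lists five drugs and secures none of these conditions. Two people following the text could extract different levels and compute different indices for the same patient.

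At stake is how well the primary outcome separates adherent from non-adherent patients. If a material share of patients take a higher-level drug, they are flagged in both arms whatever their adherence. The relative risk then moves toward 1 and power falls in a trial of 50 per arm.

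**Working it through.** **The plan's own figure.** The cut of 2 cannot be reproduced, because no unit, drug, reference level or derivation is given. No alpha, power or effect size is stated either. The sample size is only a count: 25 × 2 arms × 2 age groups = 100.

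**Step 1: what the cut means.** SD = CV × mean, so SD>2 is CV > 2/mean: 2/5 = 40%, 2/10 = 20%, 2/100 = 2%.

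**Step 2: how often a steady patient is flagged.** Assume 6 independent normal levels and a true CV of 20%. Then P(SD>2) = P(χ² with 5 df > 5 × 4/(CV × mean)²).

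| Mean level | True SD | χ² threshold | Flagged | Flagged, CV 15% to 25% |
|---|---|---|---|---|
| 5 | 1 | 20 | 0.1% | 0 to 2.5% |
| 10 | 2 | 5 | 42% | 11 to 67% |
| 15 | 3 | 2.22 | 82% | 56 to 92% |
| 100 | 20 | 0.05 | >99.9% | >99.9% |

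**Step 3: pooling two drugs.** Take three levels at exactly 7 and three at exactly 50, with no variation within either drug. The mean is 28.5 and each level is 21.5 away, so SD = √(6 × 21.5²/5) = 23.6. A perfectly steady patient is flagged.

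**Step 4: effect on the trial, one conditional illustration.**
- Control non-adherence: Section 2 gives "reports ranging from 15-40% in adults and much higher at 50-70% among adolescents". The midpoints are 27.5% and 60%. Weighted equally for "25 participants in each arm by age (13-21 years and 22 years and older) for a total of 100 participants", they give (27.5 + 60)/2 = 43.75%, about 44%.
- Intervention: half of that, about 22% (the halving is assumed).
- Also assumed: CV 20% if adherent and 45% if not, 6 levels, drug means 7 and 150, two-sided 5% tests.

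At mean 7 the Step 2 formula flags 7.0% of adherent and 84.7% of non-adherent patients. With nobody on the second drug:
- control: 0.4375 × 0.847 + 0.5625 × 0.070 = 0.410
- intervention: 0.21875 × 0.847 + 0.78125 × 0.070 = 0.240
- ratio: 0.240/0.410 = 0.585. Its distance from the true 0.50 is misclassification at mean 7, not drug mix.

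A share f on the mean-150 drug is flagged in both arms, so each rate becomes f + (1 − f) × rate. At f = 20% that is 0.528 and 0.392, ratio 0.742. Simulation (50 per arm, levels truncated at zero) agrees within about 0.01:

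| Share on mean-150 drug | RR, SD>2 | Power, SD>2 | Power, log within-drug SD adjusted for drug |
|---|---|---|---|
| 0% | 0.58 | 44% | about 40% |
| 10% | 0.67 | 36% | about 40% |
| 20% | 0.75 | 29% | about 40% |
| 30% | 0.80 | 24% | about 40% |

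Repeat runs of 4,000 to 8,000 trials per cell agreed within about 2 points. With no true difference, SD>2 rejected in 5.2% of trials at 0% and 5.6% at 20% on the second drug.

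**Step 5: sensitivity to the fixed inputs** (power, SD>2 against adjusted log SD).
- One drug at mean 10: 23% against 41%. The gap arises with no drug mix, from the fixed cut against the level.
- 3 levels per patient, 10% on the mean-150 drug: 20% against 23%.
- 12 levels, one drug at mean 7: 60% against 54%, so here SD>2 does better.

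**Step 6: all levels undetectable.** If each is recorded as zero, SD = 0, which is below 2. The patient counts as adherent, although Section 5.2.3 treats undetectable levels as a sign of an adherence problem. Log SD and CV are undefined for that patient.

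**The case against.** - **The text does not say that all five drugs enter one SD.** The drug list sits in a sentence about reviewing levels, separate from the MLVI definition. A reader might infer that the plan prescribes pooling, or that Sections 5.2.3 and 9 contradict each other. Neither is supported: the plan leaves pooling open, and the two sections are compatible but incomplete.
- **The cited sources may fix the drug and unit.** They may, but the protocol carries nothing over from them. By title both concern adult liver recipients, while this trial also enrols kidney recipients and patients from age 13.
- **The relative risk may not be the primary test.** This stands. Section 9 only says that a relative risk is noted, and Section 1.1 describes a comparison of MLVI without a cut. An unscaled SD has the same scale problem there, by an amount that depends on the test.
- **Nearly everyone may take one drug.** The documents do not say. If so, and if the level is low, the harm is small. The mean-10 case shows that a single drug does not by itself guarantee this.
- **Randomisation protects validity.** In expectation it does. A reader might infer a false-positive risk, but the no-difference check gives no support for one of any size.

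**Conclusion.** The concern holds as a scale problem in an under-specified primary outcome. That an unscaled SD and a bare cut of 2 depend on drug, unit and level is arithmetic, and confidence in it is high. Confidence does not extend to the size of the harm. The fall in power from about 44% to 24% belongs to one set of assumed levels, CVs, draws and drug shares. A reader might take it as a forecast for this trial; the documents cannot support that, because they give none of those inputs and Step 5 shows the gap shrinking or reversing under others. What can be said is that the likely harm is dilution and lost power rather than false positives, and that it grows with the share of patients on a higher-level drug. The all-zero case is a secondary gap that exists even with one drug. The documents do not show how often it would occur. The point should be fixed before analysis.

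**What to change.** Amend Sections 5.2.3 and 9:

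1. Compute the MLVI within one index drug per patient, set by a pre-specified rule. Record drug and unit, and never pool levels of different drugs into one SD. State the rule for switches and a minimum number of levels.
2. Apply SD>2 only to patients on the drug and unit for which the sponsor documents that the cut was set.
3. For the all-patient comparison between arms, use a scale-free or drug-adjusted measure. Examples are log within-drug SD with index drug as a covariate, or within-drug CV. State before unblinding whether item 2 or item 3 is primary.
4. State how patients whose levels are all undetectable are classified in the analysis.

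**Cost.** The change is analysis-plan wording and two extraction fields (drug and unit), with no new visits or tests. Item 2 alone drops patients on other drugs from 50 per arm. Item 3 can cost about 4 to 8 points of power in the assumed cases if nearly all patients take one low-level drug. Patients below the minimum number of levels need a stated handling rule.
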